**Table 2. Schedule of Assessments**

Assessments	Introductory Meeting	Session 1	Session 2	Session 3	Session 4	Refresher Session 8 wks	Follow-up 12 wks
Informed Consent	X						
Demographic/health questionnaire	X						
SF-36	X				X		X
PROMIS questionnaires	X				X		X
Sedentary Behavior interview	X				X		X
Self-efficacy questionnaire	X				X		X
Self-regulation questionnaire	X				X		X
Outcome expectations questionnaire	X				X		X
Short Physical Performance Battery	X				X		X
Accelerometers	X				X		X
Adverse events			X	X	X	X	X
Fidelity monitoring		X	X	X	X	X	
Satisfaction						X	
Feasibility						X	
Cost estimate							X

Note. Screening of prospective participants and randomization will be completed prior to the introductory meeting.

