## PRÉCIS

Title: Translating a ‘Stand Up and Move More’ Intervention by State Aging Units to Older Adults in Underserved Communities

Objectives: To examine the effectiveness of a *Stand Up and Move More* intervention to reduce sedentary behavior, increase physical activity, and improve functional performance and quality of life in older adults. A second objective is to examine the feasibility of implementing the *Stand Up and Move More* intervention by State Aging Units to underserved communities in the state.

Design and Outcomes: A randomized controlled trial will be conducted with older adults from four counties in Wisconsin (i.e., Dane, Rock, Iowa, and Vilas counties) randomized to intervention or wait-list control groups. Sedentary behavior, physical activity levels, functional performance, and health-related quality of life will be assessed at baseline (before the intervention begins), at week 4 (after the intervention), and week 12 (follow-up) to examine the effectiveness of the program. Feasibility of implementing the program by our community partners will be assessed via semi-structured interviews.

Intervention and Duration: The intervention consists of an introductory session, four weekly sessions (i.e., once/week for four weeks), and a refresher session at 8 weeks, and will be delivered by community partners in each county. Based on self-regulation theory, the sessions will elicit ideas from older adults regarding how they can reduce their sitting time, help them set practical goals, develop action plans to reach their goals, and refine their plans across sessions to promote behavior change.

Sample Size and Population: Eighty sedentary adults greater than 55 years of age from four counties made up predominantly of rural older adults and older African American adults will be randomly assigned to intervention (n = 40) or wait-list control (n = 40) groups.

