**Participants:** A power analysis was performed to estimate optimal sample size for detecting potential differences between intervention and wait-list control groups in sedentary behavior using a repeated measures design, with an alpha of 0.05, a power of 0.80, and a medium effect (0.57). Results from the G-power analysis indicated a total of 68 participants (34 per group) would be needed for the proposed study but we have increased sample size in anticipation of a potential attrition rate of approximately 20% (a minimum of 80 adults older than 55 yrs will be recruited). Four counties (Rock, Iowa, Vilas & Dane) will each recruit between 20–30 older adults who will be randomized to either the intervention group ( $n = 10–15$ ) or the control group ( $n = 10–15$ ). Inclusion criteria includes > 55 yrs, currently inactive or low active (i.e., < 60 min of physical activity/week), residents of Rock, Iowa, Vilas or Dane Counties, and residing in a home or an apartment. Exclusion criteria are low levels of sedentary behavior (i.e.,  $\leq 6$  hours/day); recent hospitalization (past month); uncontrolled medical conditions including uncontrolled hypertension (BP > 170 systolic or 100 diastolic), heart disease (symptoms of angina with minimal exertion in the past month), actively receiving chemotherapy or palliative care for cancer, stage 4 liver disease (e.g., cirrhosis with ascites or encephalopathy or history of

bleeding esophageal varices), end-stage renal disease (on dialysis or creatine > 4), or end-stage pulmonary disease (dyspnea at rest or with minimal exertion); severe arthritis or any orthopedic condition that could be made worse by standing up and moving more; inability to stand up without assistance of another person; and inability to speak or hear spoken English. Participants will be given a gift card up to \$50 upon study completion (\$20 for participating in the study plus \$10 per each of three assessments).

Recruitment of Participants: Staff from Aging Units in the four counties will recruit older adults from their counties for this study. Recruitment strategies include announcements in senior newsletters, at congregate dining sites, churches, and medical clinics. In addition, announcements will be posted on Aging Unit websites, and flyers will be sent to mailing lists of older adults in the various counties. These strategies were used in our pilot research and worked well in recruiting the estimated sample size.

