Individuals who are interested in learning more/participating in the study will be instructed to call a designated phone number and leave a message. A trained research assistant will promptly (within 48 hrs) call the prospective participant back and give a general explanation of the study, ask if the individual is still interested in participating in the study, and inquire whether they are willing to complete a brief interview (i.e., phone screen) to determine eligibility. If the individual agrees to the interview, they will be asked questions based on the inclusion/exclusion criteria. Those individuals who are deemed eligible to participate in the study will be informed of the introductory meeting (i.e., date/time and location). Individuals who are not eligible to participate in this study will be thanked for taking time to answer questions but be told that they will not be able to participate due to the strict requirements for this research.

Introductory Meeting: An introductory meeting will be held in each county for older adults interested in participating in the study. Our community partners will arrange the meeting at a location convenient for participants in their county. The PI will attend the meeting and describe the study (i.e., inform prospective participants of the procedures, risks and benefits, and they are free to discontinue participation in the study at any point). Prospective participants will be provided with ample time to read the Informed Consent Form and have the opportunity to ask and obtain an adequate reply to any questions they may have. Individuals interested in participating in the study will then sign an informed consent document and baseline assessments will be completed.

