*\*Note:* [name], our community research associate, will provide the training and fidelity monitoring of our community partners. She has been involved in statewide coordination of evidence-based health promotion programs for older adults in Wisconsin for over 9 years. Part of her responsibilities have included training, overseeing, and fidelity monitoring for health promotion programs (e.g., the “Chronic Disease Self-Management” program). In addition, [name] (co-investigator) has expertise in developing tools for fidelity monitoring for the health promotion program “Stepping On.” These fidelity tools are used nationally to ensure high fidelity with dissemination of falls prevention programs. Treatment fidelity implementation in the proposed study is consistent with NIH Behavior Change Consortium Treatment Fidelity Workgroup recommendations involving study design, training of providers, delivery of treatment, receipt of treatment, and enactment of treatment skills.

**Wait-List Control Group:** Older adults assigned to the control group will be instructed to go about their daily routines during the first 12 weeks of the study. They will complete, in the same manner as the intervention group, assessments at baseline, 4, and 12 weeks. The control participants will receive the *Stand Up & Move More* intervention after 12 weeks.

**Measures:** Data collection sessions will be held the week prior to beginning the intervention (at the introductory meeting), at 4 weeks (following the delivery of the intervention), and at 12 weeks (follow-up) at readily accessible sites in each county (see Appendices for a summary table of outcomes assessment). Assessments will be completed by assessors trained by [name]. The assessors will be blinded to group assignment, and every effort will be made to ensure the assessors remain blinded throughout the duration of the study.

**Sedentary behavior** will be assessed both subjectively and objectively: **(a)** Participants will be interviewed by the investigators about their time spent sitting during the day in different activities (e.g., watching TV, reading) over the past week using a previously validated questionnaire for older adults; **(b)** Activity Monitors will be worn at each assessment for one week: The *activPAL*

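### Randomisation is scheduled before consent and before the baseline monitor week, with no rule for counting people who then decline

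*Combined protocol and SAP*

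**What the plan says.** The only statement of when randomisation happens is the note under Table 2 (Supplements): "Screening of prospective participants and randomization will be completed prior to the introductory meeting". The Précis and the Design and Participants paragraphs describe randomisation but do not time it.

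Before the meeting there is only a telephone screen (Recruitment of Participants): "If the individual agrees to the interview, they will be asked questions based on the inclusion/exclusion criteria". At the meeting the study is described, and "Individuals interested in participating in the study will then sign an informed consent document and baseline assessments will be completed" (Introductory Meeting). Table 2 marks consent, questionnaires, the SPPB and accelerometers in that same column.

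On timing, Measures says "Data collection sessions will be held the week prior to beginning the intervention (at the introductory meeting", and also "Activity Monitors will be worn at each assessment for one week". On blinding, it says "The assessors will be blinded to group assignment"; nothing comparable is said of participants or recruiters.

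On numbers, the Précis says the eighty adults "will be randomly assigned to intervention (n = 40) or wait-list control (n = 40) groups", and Participants says "a minimum of 80 adults older than 55 yrs will be recruited".

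**The concern.** Followed as written, the order is phone screen, randomisation, consent, baseline. Three things follow whoever knows the allocation. People are allocated before they have agreed to take part. Those who decline or do not attend have already been randomised, with only phone-screen information on them. The activPAL baseline, which is both the first trial of the 2 x 3 ANOVA and the covariate in the longitudinal models (Analyses), is recorded after allocation.

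A further problem arises only if participants or recruiters know the allocation by then. Refusal could then differ by arm, which undoes the comparability that randomisation provides. A participant who knows the group could also start to sit less, or behave otherwise differently, during the baseline week. Blinded assessors cannot prevent that, because the outcome is the participant's own behaviour.

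**Working it through.** **1. Sequence.**

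| Step | Source | Position relative to the introductory meeting |
|---|---|---|
| Phone screen | Recruitment of Participants | before |
| Randomisation | Table 2 note | before |
| Consent | Introductory Meeting; Table 2 | at |
| Questionnaires, SPPB | Introductory Meeting; Table 2 | at |
| activPAL wear, one week | Measures; Table 2 | starts at, ends after |
| Session 1 | Measures; Table 2 | within about a week after |

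No section gives a different order.

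**2. Room to disclose allocation after baseline.** Intervention participants must know their group by Session 1. If the interval from the meeting to Session 1 is exactly 7 days (an assumption), 7 - 7 days of wear = 0 days remain. Disclosure before or during the wear week is therefore a live possibility.

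**3. The plan's own sample size.** Inputs from Participants: alpha 0.05, power 0.80, effect 0.57, 68 in total, about 20% attrition. A between-group F test with 2 groups and m = 3 measurements has f = 0.57/2 = 0.285 and noncentrality N x f² x m / (1 + (m - 1) x rho). With rho = 0.5 (assumed; none is given), N = 68 has power 0.810, so the stated 68 reproduces.

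**4. Effect of losses between randomisation and consent.** Let r be the pre-consent loss (assumed; the documents give none), with the plan's 20% attrition applied to those who consent.

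- Completers = N x (1 - r) x 0.8
- Number to randomise for 68 completers = 68 / (0.8 x (1 - r)), rounded up

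| r | Consent, of 80 | Complete, of 80 | Power (same F test) | Complete, of 120 | Randomise to keep 68 |
|---|---|---|---|---|---|
| 0% | 80 | 64.0 | 0.785 | 96.0 | 85 |
| 5% | 76 | 60.8 | 0.763 | 91.2 | 90 |
| 10% | 72 | 57.6 | 0.740 | 86.4 | 95 |
| 20% | 64 | 51.2 | 0.687 | 76.8 | 107 |

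The 120 column is the top of the planned county range, 4 x 30. A workshop arm of 10 becomes 10 x 0.9 = 9 at 10% loss and 10 x 0.8 = 8 at 20%, below the planned 10-15.

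**5. Illustration of baseline bias, only if allocation is known.** Take the pilot's 60 min/day reduction as the true effect and suppose the intervention arm already sits s = 10 min/day less in the baseline week (assumed).

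- Change score: -60 - (-10) = -50 min/day.
- Covariate-adjusted: -60 + slope x 10 = -57, -55 or -52 min/day for slopes 0.3, 0.5 or 0.8 (assumed).

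Each 10 min/day of shift in this direction understates the benefit by 10 min/day or by 3-8 min/day respectively. The documents give neither the shift nor the slope.

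**The case against.** The strongest reply is that measuring baseline after allocation does no harm while the allocation is unknown, and some text leans that way. Eligible callers are to be told the date, time and place of the meeting, with no mention of group. The principal investigator, who runs the meeting, is also listed with the blinded data collectors, so announcing groups there would break the plan's own blinding. This is fair, and the baseline bias is therefore conditional. But no concealment is described. Community partners both recruit and run the workshops (Data Management), so they need group lists, and nothing covers the wear week.

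On numbers, 80 is a minimum, and Potential Problems and Alternative Strategies allows extra workshops or counties if recruitment falls short. At 120 randomised, the 68 is met even with 20% refusal. The gap between 64 and 68 with no refusals is a separate matter: 80 was set where 20% attrition needs 85. If refusals were meant to fall within the 20%, the added loss would be nil. All of this limits the claim about power. None of it corrects the order or says how refusals are counted.

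Multiple imputation for missing data and attrition is the nearest existing rule. It does not say whether someone who never consented belongs in the analysis, and such a person has no baseline data to impute from.

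The Table 2 note may simply be loosely worded. If so, it still needs correcting, at less cost.

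**Conclusion.** The concern holds and should be settled before any county randomises, because the order cannot be repaired in the analysis. That allocation precedes consent and baseline wear follows directly from the text and rests on no assumption; nor does the absence of a rule for people who decline.

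The size of the loss depends on an unknown refusal rate. At an assumed 10% with 80 randomised, completers fall from 64 to about 58 and power from 0.785 to 0.74 (correlation 0.5 assumed). With recruitment near 120, the shortfall against 68 disappears but the counting problem does not.

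Bias in the baseline or in who consents depends on participants or recruiters knowing the allocation, which the documents leave open. If it stays undisclosed until wear is complete, the baseline bias goes and the consent order and refusal count remain as problems.

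**What to change.** Reorder the sequence and the Table 2 note as follows:

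1. Phone screen.
2. Introductory meeting, with consent, questionnaires, SPPB and issue of monitors.
3. Baseline monitor week.
4. Randomisation within each county, with the planned blocking for age.
5. Notification of group before Session 1.

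Define the intention-to-treat set as everyone randomised under this sequence. State in Design and Introductory Meeting when randomisation and disclosure occur.

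If randomisation cannot move, the minimum is to conceal allocation from participants, recruiters and assessors until consent and baseline wear are complete, report refusals by arm, and state how they are counted.

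The cost is wording in Design, Introductory Meeting, Measures and the Table 2 note, and a few more days between the meeting and Session 1 in each of the four counties. Participants get shorter notice of their group, and 20-30 people per county must be notified. No extra visit is needed if randomisation waits only for the wear week to elapse and not for the monitors to be read. The concealment fallback needs the same few days.
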